5.2.1 Rescue Medication

Fluconazole will be used as rescue medication in this investigation, and patients will receive a prescription for fluconazole if considered necessary to relieve their VVC symptoms on Day 14. Patients withdrawing at any point in the investigation may receive fluconazole if considered necessary by the Investigator. The dose of fluconazole will be decided by the Investigator on an individual basis. The use of rescue medication will be recorded in the eCRF.

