5.7 Prior and Concomitant Medication

Information about any concomitant medication, including OTC medications and vitamins taken by patients during the study and within 14 days prior to inclusion shall be documented in the eCRF. The generic name or trade name, dosage, and reason for use shall be recorded for all medications.

NOTE: Antifungal medication during the study and within 14 days prior to inclusion is strictly prohibited

See [Appendix 1, Section 3](#) for specific questions.

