6.1.2 Patient Questionnaire

The questionnaire can be found in [Appendix 1](#).

The Clinical Trial Unit will call the patients on Day(s) 4, 14 and 35; or Day(s) 4, 11, 21, and 42 if receiving prolonged treatment; and ask questions from the patient questionnaire relating to vulvovaginal symptoms (itching, burning, or irritation), usability, concomitant medications, and AEs, if any.

Questions from *Section 1* in the patient questionnaire relating to vulvovaginal symptoms of itching, burning, and irritation will be asked to patients over telephone on Day(s) 4, 14, and 35; or Day(s) 4, 11, 21, and 42 if receiving prolonged treatment. A recurrence question will be asked to patients at Days(s) 14 and 35 if not receiving prolonged treatment and at Days(s) 21 and 42 if receiving prolonged treatment.

Questions from *Section 2* in the patient questionnaire relating to usability in will be asked to patients on Day 7, and Day 14 if receiving prolonged treatment.

Questions from *Section 3* and *Section 4* in the patient questionnaire relating to concomitant medications and AEs, respectively, will be asked to patients at each visit/telephone contact.

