Appendix 1 Patient Questionnaire

Section 1. Vulvovaginal Symptoms

Day(s) 0, 4, 7, 14, and 35; or Day(s) 0, 4, 7, 11, 14, 21 and 42 if receiving prolonged treatment. Questions will be asked by the Investigator at Day(s) 0, 7, and 14 (for patients receiving prolonged treatment); and by the Clinical Trial Unit at remaining days.

Scoring of symptoms

	0 = none (absent)	1 = mild (slight)	2 = moderate (definitely present)	3 = severe (marked, intense)
Irritation				
Itching				
Burning				

The question “Have the symptoms returned, so that you need to seek medical care?” (yes/no) will be asked at Day(s) 14 and 35 if not receiving prolonged treatment and at Day(s) 21 and 42 if receiving prolonged treatment.

Section 2. Usability

Day 7 and Day 14 if receiving prolonged treatment:

Is the vaginal tablet easy to use?

- Yes
- No
- If no, provide reason: _____

Do you find the use of the vaginal tablet gentle?

- Yes
- No
- If no, provide reason: _____

Is the treatment odor free?

- Yes
- No

Is the treatment smear-free and dripless?

- Yes
- No

How do you generally regard the treatment?

1	2	3	4	5	6	7	8	9	10
Not satisfied					Very satisfied				

Section 3. Concomitant Medications

Day(s) 4, 7, 14, and 35; or Days(s) 4, 7, 11, 14, 21, and 42 if receiving prolonged treatment); patients will be asked: “since the last study visit or telephone contact, have you changed dose or taken any new medication?”

Section 4. Adverse Events

The following question will be asked at each patient contact: “since the last visit / telephone contact, have you had any health problems?”

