#### 7.1.4 *Analysis visit*

An analysis visit is defined as a categorical variable used to classify values within an analysis variable into temporal or conceptual groups used for analyses.

The visits as defined in the case report form, CRF, will be used as analysis visits.

In general, data from unscheduled visits will be presented in data listings only and not included in analysis or summary tables. An exception to this is data used to confirm eligibility in association with screening or randomisation where the last assessment will be considered in summaries of screening data.

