#### 7.1.5 *Handling of missing data*

The statistical analysis will be based on the observed data, i.e. no imputation is planned. In case of one or more missing value(s) among the 6 items included in the calculation of the CVVS score, the CVVS score will remain missing. In case of one or more missing symptom value(s) in the 3 vulvovaginal symptom items (itching, burning, and irritation), the sum of the 3 vulvovaginal symptoms scores will be set to missing. See also [Sections 8.6 and 8.7](#) below.

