### 7.2.2 *Per-protocol analysis sets*

Per Protocol (PP) Population 1 (PPAS Clinical Cure) - This will include all FAS patients without any major protocol deviation, i.e. patients who have completed the study and sufficiently complied with the study protocol, have available primary endpoint data and have received the study treatment according to protocol. The final definition of a major protocol deviation will be decided and defined at the clean file meeting and documented in the clean file report. If a relevant number of patients are excluded from the PP population, then the analysis of the primary clinical performance endpoint will be provided for the PP population. The main purpose with this analysis set is to analyse the primary endpoint, i.e. Clinical Cure.

Per Protocol (PP) Population 2 (PPAS Recurrence) - In addition to what was specified in the CIP, a second Per-protocol analysis set will be defined with the main purpose of analysing recurrence. The rationale for this is that the different recurrence rate analyses are regarded as important to also perform using a “per protocol” approach. The main purpose with this per protocol dataset is thus to analyse Recurrence. This population will constitute a sub-population from PP population 1 defined

above, and will be defined in similarity with this population, but instead based on the secondary recurrence rate endpoints. The final definition of a major protocol deviation with respect to these secondary endpoints, will be decided and defined at the clean file meeting and documented in the clean file report.

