### ***8.8 Recurrence rate***

Recurrence rate is based on a binary variable, where a recurred patient is defined as a patient clinically cured on Day 7 and thereafter responding “yes” at specified follow-up visits to a yes/no question from the patient questionnaire on whether the symptoms have recurred.

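### Recurrence is counted only from a yes at scheduled contacts, so a relapse that is treated or leads to withdrawal between contacts can count as no recurrence

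*SAP*

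**What the plan says.** **Event.** Under SAP 8.8 a recurred patient was cured on Day 7 and later says yes "at specified follow-up visits to a yes/no question from the patient questionnaire on whether the symptoms have recurred". Protocol 6.1.2 fixes the contacts: "A recurrence question will be asked to patients at Days(s) 14 and 35 if not receiving prolonged treatment and at Days(s) 21 and 42" for those on prolonged treatment. The question in Protocol Appendix 1 is "Have the symptoms returned, so that you need to seek medical care". SAP 3.2.1 bases the Day 21 and Day 42 rates on Day 14 cure, which SAP 8.8 does not mention.

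**Treatment of a relapse.** Protocol 5.7 states: "Antifungal medication during the study and within 14 days prior to inclusion is strictly prohibited". Protocol 5.2.1 gives two routes to fluconazole. One is a prescription on Day 14, with no withdrawal required. The other is: "Patients withdrawing at any point in the investigation may receive fluconazole if considered necessary by the Investigator". The flow chart text in Protocol 3.1 attaches Day 14 fluconazole to the prolonged-treatment group.

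**Missing and off-schedule data.** SAP 7.1.5: "The statistical analysis will be based on the observed data, i.e. no imputation is planned". SAP 7.1.1 keeps patients with missing data in percentage denominators unless stated otherwise. SAP 7.1.4 says that, in general, "data from unscheduled visits will be presented in data listings only and not included in analysis or summary tables".

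**Per-protocol set for recurrence.** SAP 7.2.2: "This population will constitute a sub-population from PP population 1", and PP population 1 is limited to patients who completed the study and complied sufficiently.

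**The concern.** Neither document counts antifungal treatment of VVC, or withdrawal because VVC has returned, as a recurrence. Yet these are what may follow when a relapse is bad enough to need treatment. The event definition therefore risks missing the relapses that matter most, and the missing-data rules do not recover them.

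Relapse after existing treatments is part of the protocol's case for the product (Protocol 1.1). The SAP considers the recurrence analyses important enough to create a second per-protocol set for them (SAP 7.2.2 and 7.11). Protocol 9 says that if missing data are an issue, bias should be reduced or, failing that, pointed in the conservative direction. The SAP contains no such measure for recurrence.

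**Working it through.** **1. What there is to reproduce.** The documents state no expected recurrence rate, precision or power. The only design figure borrowed here is the 70% cure rate from the sample size statement. That statement reproduces by the normal approximation: n = ((1.645 × √(0.4 × 0.6) + 1.282 × √(0.7 × 0.3)) / 0.3)² = 21.56, rounded up to 22.

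**2. Tracing one patient.** Take a woman cured on Day 7 who answers no on Day 14 and relapses on Day 20. The next question comes on Day 35, 35 − 14 = 21 days after the last one. After prolonged treatment the gap is the same (42 − 21 = 21).

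- *She withdraws and is treated.* If no further answer is obtained, she has no Day 35 value. Nothing is imputed, she stays in the default denominator, and she contributes no event. An answer taken at exit might exist, but no SAP rule brings it into the rate.
- *She treats herself and stays in.* On Day 35 she is well and can truthfully say no. She is counted as not recurred.
- *PPAS Recurrence.* On the first route she did not complete the study. On the second she took a banned medicine, and whether that is a major deviation is left to the clean file meeting. The set may exclude her either way.

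**3. Size, under stated assumptions.** Number cured on Day 7: 24 × 0.70 = 16.8, taken as 17. True relapse: 13% to 26% at 30 to 35 days, from the note under Protocol Table 1 (azole-treated severe VVC, so only a rough guide). This gives 0.13 × 17 = 2.2 to 0.26 × 17 = 4.4, that is, 2 to 4 recurrences. The number lost is not given anywhere and is varied over its whole range. Intervals are two-sided 95% Clopper-Pearson, as in SAP 7.9.2.

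| Lost, of 4 true recurrences | Missing kept in denominator (SAP 7.1.1 default) | Lost patients dropped from denominator |
|---|---|---|
| 0 | 4/17 = 23.5% (6.8–49.9) | 4/17 = 23.5% (6.8–49.9) |
| 1 | 3/17 = 17.6% (3.8–43.4) | 3/16 = 18.8% (4.0–45.6) |
| 2 | 2/17 = 11.8% (1.5–36.4) | 2/15 = 13.3% (1.7–40.5) |
| 3 | 1/17 = 5.9% (0.1–28.7) | 1/14 = 7.1% (0.2–33.9) |
| 4 | 0/17 = 0% (0–19.5) | 0/13 = 0% (0–24.7) |

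Each lost recurrence costs 1/17 = 5.9 percentage points under the default. A self-treating patient who answers no stays in the denominator under either rule. With 2 true recurrences the default rate falls from 2/17 = 11.8% to 1/17 = 5.9% if one is lost, and to 0/17 if both are. Counting treated and withdrawn recurrences as events restores 4/17 (or 2/17).

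**The case against.** Several objections have force.

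- *Rescue does not always require withdrawal.* Protocol 5.2.1 allows a Day 14 prescription without it, and a relapse reported at the Day 14 call counts as a yes. A reader might infer that a relapsing patient can be treated only by leaving the study; the text does not say that. The withdrawal-only route applies outside Day 14, which still covers most of the period behind the Day 21, 35 and 42 rates.
- *Loss at exit is not certain.* Protocol 4.6 asks for end-of-study assessments at withdrawal wherever possible, and 3.6 for a telephone questionnaire from patients who refuse visits. No text classes these as unscheduled visits, and SAP 7.1.4 is hedged. This stands, but the SAP never says that such answers enter the rate.
- *SAP 8.8 can be read cumulatively.* It does not clearly tie the Day 35 rate to the Day 35 answer alone. A woman who relapsed and recovered might also still say yes. Both points show ambiguity, which the definition should remove.
- *Other errors may push the rate up.* The follow-up contacts are by telephone, without examination, microscopy or culture, so returned symptoms from another cause count as recurrence. Protocol 1.1 reports that only 34% of women buying over-the-counter antimycotics for VVC had it. The documents therefore do not support a claim about the net direction of bias.
- *The information is displayed elsewhere.* Concomitant medications and withdrawal reasons are tabulated, and rescue dates are listed. That helps a careful reader but does not correct the reported rate.
- *The stakes are limited.* This is a secondary endpoint without testing in a 24-patient feasibility study, and the illustrative intervals overlap heavily.

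**Conclusion.** The concern holds as a weakness of the recurrence definition. As written, SAP 8.8 together with 7.1.1 and 7.1.5 can count a cured patient who relapsed and was treated, or who left, as not recurred. PPAS Recurrence may remove her altogether. Error from this route can only lower the rate: by 5.9 points per lost recurrence if 17 patients are cured, and by nothing if every recurrence is recorded.

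It would go too far to say that the reported rate is biased low. How many recurrences would be lost cannot be known from the documents, and unconfirmed telephone answers may act the other way. It would also be wrong to say that the plan shrinks the denominator, because the SAP default keeps these patients in. The illustration rests on 17 cured patients and on a relapse range from a different treatment and a more severe population. The Day 7 cure analysis and its conclusion are unaffected.

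**What to change.** Rewrite SAP 8.8 as follows.

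- Define recurrence cumulatively: by Day 14 and by Day 35 from Day 7 cure, and by Day 21 and by Day 42 from Day 14 cure.
- Count as recurred any patient who, after cure and up to that day, (a) answers yes at any contact, including answers taken at early withdrawal; or (b) starts any antifungal for VVC; or (c) withdraws because VVC symptoms have returned.
- For (b), search all concomitant medication. SAP 7.7 identifies rescue only by the recorded indication of rescue medication and could miss self-treatment. State how fluconazole issued at the Day 14 visit to a patient scored as cured at that visit is counted.
- State the denominator, and say that exit answers are used notwithstanding SAP 7.1.4.
- Do not exclude a patient from PPAS Recurrence for an antifungal or a withdrawal that is itself the recurrence. Because this set sits inside a completers-only set, SAP 7.2.2 needs a matching change.
- Keep the yes-only rate as a secondary display.

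Separately, Protocol 5.2.1 and the flow chart text must be reconciled on which patients the Day 14 fluconazole route covers.

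The cost is SAP wording and a few lines of programming on data already collected: concomitant medication at each contact, rescue use and reasons for withdrawal. Patient management does not change. The downside is a less favourable rate that may include some self-diagnosed episodes, which is why the yes-only display should stay beside it.

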### ***8.9 Proportion of patients receiving prolonged treatment***

The proportion of patients receiving prolonged treatment is based on a binary variable which indicate whether a patient has received prolonged treatment or not, i.e. received study treatment on at least one of the days 7, 9, 11, or 13.

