Name of Products: Gedea Pessary (commercial name pHyp)
Name of Active Ingredient: Glucono-delta-lactone (GDL) and sodium gluconate (NaG)
Title of Study: An open-label study to evaluate clinical performance of Gedea Pessary in adult women with vulvovaginal candidiasis (VVC).
Clinical Investigation Plan Number: QRS-CL1-003
Investigators and Study Center(s): NAME , VO Kvinnosjukvård, Skånes universitetssjukvård, Lund, Sweden NAME , Annerokliniken, Löddeköpinge, Sweden NAME , Hoftekliniken, Helsingborg, Sweden Kliniska prövningssenheten, Kliniska Studier Sverige - Forum Söder, Skånes universitetssjukhus, Lund, Sweden
Classification of Trial: Feasibility Clinical Investigation
Objectives: To investigate the clinical performance, tolerability, and safety of the investigational product.
Methodology: This is an open-label, single-armed, multi-center study to evaluate clinical performance, tolerability, and safety of Gedea Pessary in 24 adult women with VVC. On Day 0, patients will have gynecological examination, vaginal samples taken, and will receive the investigational product to be self-administered 2 days apart (Day[s] 0, 2, 4, and 6). Patients will be examined after 7 days with respect to VVC signs and symptoms and if not cured, will receive prolonged treatment on Day(s) 7, 9, 11, and 13. Patients will be followed-up by telephone up to 29 days after last treatment. Vaginal samples will be used for confirming diagnosis and microbiome analyzes. Patient questionnaires will be used for assessing VVC symptoms, usability, and adverse events (AEs).
Number of Subjects Planned: Twenty-four (24) patients
Diagnosis and Main Criteria for Inclusion: Inclusion Criteria: 
• Adult, post-menarchal, pre-menopausal women aged 18 years or older

- Diagnosis of VVC, defined as having a white or creamy vaginal discharge plus the following findings:
 1. At least 2 of the following signs and symptoms of VVC that are characterized as at least moderate: itching, burning, irritation, edema, redness, or excoriation.
 2. Potassium hydroxide (KOH) or saline preparation from the inflamed vaginal mucosa or secretions revealing yeast forms (hyphae or pseudohyphae) or budding yeasts.
- Having decisional capacity and providing written informed consent
- Negative urine pregnancy test at screening
- Refrain from using any intravaginal products (i.e., contraceptive creams, gels, foams, sponges, lubricants, or tampons, etc.) during the study period

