3.5.5 Day 7 (+2 Days); Follow-up Visit

Patients will visit the clinic on Day 7 to have gynecological examination performed. The Investigator or an authorized designee will assess the presence of vulvovaginal signs (erythema, edema, or excoriation) and symptoms (itching, burning, or irritation) and score each sign and symptom.

Vaginal samples will be examined by microscope to reveal yeast forms (hyphae or pseudohyphae) or budding yeast and secretion samples collected by swab to be used for sequencing analysis of the vaginal microbiome. Vaginal pH will also be assessed.

If VVC symptoms are still present, patients will have prolonged treatment and receive additional doses of investigational product to be administered at home on Day(s) 7, 9, 11, and 13.

In addition, patients will be asked questions from the patient questionnaire to assess: usability; concomitant medications; and AEs, if any.

Procedures performed:

- Gynecological examination by Investigator or authorized designee evaluating signs (erythema, edema, or excoriation) and symptoms (itching, burning, or irritation of VVC according to the scoring scale
- Fungal KOH microscope assessment
- Vaginal swab for sequencing
- Vaginal pH
- Recording of:
 - concomitant medications,
 - adverse events, and
 - usability
- Treatment dispensing and self-administration by patients if receiving prolonged treatment

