#### 7.1.3 *Analysis relative day*

The analysis relative day for an assessment/value is defined as the time in days from the date of first administration of treatment to the date of the assessment. The date of first administration of treatment is considered as day 0.

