### 7.2.1 *Full analysis set*

Full Analysis Set (FAS): This is the primary population and comprises all patients entering the study and having received at least 1 dose of study treatment. Analyses of clinical performance will be performed against this population.

In addition to this, two sub-populations based on this FAS will be formed: “FAS (For patients not receiving prolonged treatment)”, and “FAS (For patients receiving prolonged treatment)”.

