## 7.8 Compliance

Patients will be asked about investigational product administration by telephone on Day 4 and at the site on Day 7, and also on Day(s) 11 (telephone) and 14 (site) if receiving prolonged treatment. No other measurements of treatment compliance will be made. These compliance data will be summarised for the full analysis set. The rate of compliance is defined as the actual amount of study treatment taken divided by the expected amount of study treatment to be taken. The expected amount is based on the planned duration of treatment (*i.e.* for prematurely withdrawn patients, the expected amount is computed as if the patient had not withdrawn). The expected amount is 4 doses for patients without prolonged treatment and 8 doses for patients with prolonged treatment.

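### SAP 8.9 identifies prolonged treatment by dose day alone and, read literally, misclassifies a late fourth pessary and a Day 8 start with two-day spacing

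*SAP*

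**What the plan says.** SAP 8.9 derives the variable behind secondary endpoint v. A patient counts as prolonged if she "received study treatment on at least one of the days 7, 9, 11, or 13". The section does not mention the Day 7 decision, dispensing, the number of doses or a tolerance for late doses.

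The protocol synopsis has the first course "self-administered 2 days apart (Day[s] 0, 2, 4, and 6". The second course is handed out at the visit headed "Day 7 (+2 Days); Follow-up Visit", which may therefore fall on Day 7, 8 or 9. Protocol 3.5.5 nevertheless describes the second course as "additional doses of investigational product to be administered at home on Day(s) 7, 9, 11, and 13".

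SAP 7.1.3 numbers days from the first dose: "The date of first administration of treatment is considered as day 0". SAP 7.2.1 adds that "two sub-populations based on this FAS will be formed", one with and one without prolonged treatment, but does not say which variable forms them. SAP 7.9.2 reports endpoint vii for patients without prolonged treatment (group B) and endpoints viii to xiv for patients with it (group C).

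**The concern.** Whether a patient received a second course is a matter of fact, settled at one visit. SAP 8.9 replaces that fact with a list of days. The list matches the second course only if every first-course dose is on time and the extension starts on a listed day. The protocol allows the dispensing visit to be late and gives no dosing window for the first course, so neither condition is assured.

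Endpoint v is directly exposed. Groups B and C are exposed only if the 8.9 variable is also used to form the sub-populations. In that case a wrongly flagged patient would leave the Day 14 and Day 35 recurrence analysis. She would enter a group whose Day 14 gynecological examination she was never scheduled to have. A patient wrongly missed would drop out of the Day 11, 14, 21 and 42 analyses for which she has data.

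**Working it through.** SAP 8.9 states no figure of its own to reproduce. The check applies its rule to lists of dose days.

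**Inputs**
- Rule set S = {7, 9, 11, 13} (SAP 8.9). A patient is flagged if any dose day is in S.
- First course planned on Days 0, 2, 4, 6 (protocol synopsis).
- Dispensing visit on Day 7, 8 or 9 (protocol 3.5.5). The second course cannot start before it.
- First dose on the day of the first visit (SAP 7.1.2). Days counted from the first dose and from the visit then coincide, so the results below do not depend on which count is used.
- N = 24 and an assumed cure rate of 70% (SAP 5.1).

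**Step 1. No extension given, first course on time or late**

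| Dose days | Days in S | Result under 8.9 | Correct? |
|---|---|---|---|
| 0, 2, 4, 6 | none | not prolonged | yes |
| 0, 2, 4, 7 | 7 | prolonged | no |
| 0, 2, 5, 7 | 7 | prolonged | no |
| 0, 3, 5, 7 | 7 | prolonged | no |
| 0, 2, 4, 8 | none | not prolonged | yes |
| 0, 2, 4, 9 | 9 | prolonged | no |

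A fourth dose one or three days late triggers the flag; one that is two days late does not.

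**Step 2. Extension given, first course on time**

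| Visit day | Extension doses | Days in S | Result under 8.9 | Correct? |
|---|---|---|---|---|
| 7 | 7, 9, 11, 13 | all four | prolonged | yes |
| 8, then two days apart | 8, 10, 12, 14 | none | not prolonged | no |
| 8, then the listed dates left | 9, 11, 13 | 9, 11, 13 | prolonged | yes |
| 9, then two days apart | 9, 11, 13, 15 | 9, 11, 13 | prolonged | yes |

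Only the Day 8 start with two-day spacing is missed.

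**Step 3. Size of one error**
- Expected number prolonged at 70% cure: 24 × (1 − 0.70) = 7.2, about 7.
- One patient moves endpoint v by 1/24 = 4.2 percentage points. Starting from 7/24 = 29.2% (two-sided 95% Clopper-Pearson interval 12.6% to 51.1%), it becomes 6/24 = 25.0% (9.8% to 46.7%) or 8/24 = 33.3% (15.6% to 55.3%).
- In a group C of 7, one patient is 1/7 = 14%.

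**Step 4. Range under assumed frequencies**

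The documents give no frequencies, so these are assumptions. Let *a* be the share of the 24 × 0.70 = 16.8 patients without extension whose late dose falls on a day in S, from 0 to 20%. Let *b* be the share of the 7.2 prolonged patients who dose on 8, 10, 12, 14, from 0 to one third.

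Expected proportion flagged = (7.2 + 16.8*a* − 7.2*b*) / 24

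- *a* = 0, *b* = 1/3: (7.2 − 2.4)/24 = 20%
- *a* = 0.20, *b* = 0: (7.2 + 3.36)/24 = 44%
- *a* = 0.20, *b* = 1/3: 8.16/24 = 34%, of whom 3.36/8.16 = 41% had no extension

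The true value is 30% throughout. In the last case the two errors largely cancel in the total while the membership of the flagged group is badly mixed.

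**Step 5. A flag based on the second course**

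A patient is flagged if she was dispensed the second course at the Day 7 (+2) visit and took at least one dose of it. All ten rows above are then classified correctly.

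**The case against.** The best defence is that Days 7, 9, 11 and 13 are simply the documents' name for the extension course, so that SAP 8.9 means the planned doses and not calendar days. That is plausible. SAP 8.9 does not refer to the day count in 7.1.3, and protocol 5.8 only has patients asked about administration, so dose dates may not be recorded at all. But 8.9 does not say that the days are nominal. SAP 7.1.4 does not supply that reading either: it says "The visits as defined in the case report form, CRF, will be used as analysis visits", and Days 9 and 13 are dosing days without a visit. If dose dates are not recorded, the rule cannot be applied as written.

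It can also be said that the split is settled elsewhere. The flow-chart text in SAP section 4 divides patients by cure at Day 7, SAP 7.2 assigns analysis sets at the clean file meeting, and SAP 8.8 ties recurrence to Day 7 cure. This stands as a limit: an effect on groups B and C is an inference, because 7.2.1 does not cite 8.9. It does not repair endpoint v. Nor is cure an exact substitute for the flag, because protocol 3.5.5 triggers the extension by remaining symptoms, whereas cure allows a score of up to 3. Those passages also need to be reconciled.

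A reader might infer more than the documents support:
- **Visit windows in general break the rule.** They do not. Protocol 3.5.3 and 3.5.7 hold the dose on Day 4 and Day 11 even when the call is late. Only the Day 7 (+2) window matters, and only in one pattern.
- **A first pessary inserted the next day shifts every later day.** SAP 7.1.2 and protocol 3.5.1 place the first dose on the day of the first visit.
- **The compliance denominator is wrong for late visits.** SAP 7.8 says "The expected amount is 4 doses for patients without prolonged treatment and 8 doses for patients with prolonged treatment". It bases this on the planned duration by design and attaches no threshold to the result.
- **Late visits are likely because recruitment spans the year-end.** Protocol section 12 gives planned dates only, and nothing in the documents describes visit timing.

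**Conclusion.** The point holds in a limited form. Taken literally, the stated rule gives a wrong answer for a fourth first-course dose taken on Day 7 or Day 9 without an extension, and for an in-window Day 8 start followed by two-day spacing. The other patterns checked are classified correctly.

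Each error shifts endpoint v by 4.2 percentage points, well inside its confidence interval at N = 24. It shifts group C by about one patient in seven, provided that the same flag forms the sub-populations. The figure of about 7 patients rests on the 70% planning assumption. How often the failing patterns occur is unknown.

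The Day 7 cure rate in the full analysis set does not use the flag and is unaffected. SAP 7.9.2 plans confidence intervals and no hypothesis tests for binary secondary endpoints, so no formal conclusion turns on it. The wording should still be corrected, because the definition is wrong as stated and the change is small.

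**What to change.** In SAP 8.9, define prolonged treatment as having been dispensed the prolonged course at the Day 7 (+2) visit and having taken at least one dose of it, whatever the calendar day. In SAP 7.2.1, state that this same flag forms the two sub-populations of the full analysis set, and record the change in SAP 7.11.

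The cost is small but not nil. Protocol 5.1.1 places the dispensing logs at the study sites, and neither document shows that dispensing by pack or individual dose dates are in the analysis database. The sponsor must confirm that dispensing at the Day 7 visit is in the eCRF, or transfer it from the site accountability logs.

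Separately, the fixed dose dates in protocol 3.5.5 and the +2-day window of the same visit must be reconciled by the sponsor. No schedule is proposed here.
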